9.2 Study Management

Principal Investigator

The Principal Investigator is responsible for performing the following tasks:

1. Coordinating, developing, submitting, and obtaining approval for the protocol as well as its subsequent amendments.
2. Assuring that all participating institutions are using the correct version of the protocol.
3. Taking responsibility for the overall conduct of the study at all participating institutions and for monitoring the progress of the study.
4. Reviewing and ensuring reporting of Serious Adverse Events (SAE).
5. Reviewing data from all sites.

Coordinating Center

The UPMC Hillman Cancer Center Coordinating Center is responsible for performing the following tasks:

1. Ensuring that IRB approval has been obtained at each participating site prior to the first patient registration at that site, and maintaining copies of IRB approvals from each site.
2. Managing central patient registration.
3. Collecting and compiling data from each site.
4. Establishing procedures for documentation, reporting, and submitting of AE's and SAE's to the Protocol Chair, and all applicable parties.
5. Facilitating audits by securing selected source documents and research records from participating sites for audit.

Participating Sites

We currently estimate participation of 3 sites. Participating sites are responsible for performing the following tasks:

1. Following the protocol as written, and the guidelines of Good Clinical Practice (GCP).
2. Submitting data to the Coordinating Center.
3. Registering all patients with the Coordinating Center by submitting patient registration form, signed informed consent, and all required documentation promptly
4. Providing sufficient, experienced clinical and administrative staff and adequate facilities and equipment to conduct a collaborative trial according to the protocol.
5. Maintaining regulatory binders on site and providing copies of all required documents to the Coordinating Center.
6. Collecting and submitting data within 10 days.

Staffing

UPMC Hillman Cancer Center Coordinating Site - Staffing will include a Clinical Research Manager, Clinical Research Coordinator and Research Associate. The participating sites will provide experienced staff, and adequate equipment and facilities to support this clinical trial. The participating sites will also be responsible for research staff training in computer

applications, human subject research, and HIPAA compliance, as well as the continuing education in these areas as required by local institutional standards.

Documentation

Each participating site is responsible for submitting copies of all relevant regulatory documentation to the Coordinating Center. The required documents include, but are not limited to the following: local IRB approvals (i.e., protocol, consent form, amendments, patient brochures and recruitment material, etc.), IRB membership rosters, summary of unanticipated problems or protocol deviations, and documentation of expertise of the investigators. The Coordinating Center will provide each participating site with a comprehensive list of the necessary documents. It is the responsibility of the participating sites to maintain copies of all documentation submitted to the Coordinating Center.

Confidentiality

All unpublished information that the Coordinating Center gives to the investigator shall be kept confidential and shall not be published or disclosed to a third party without the prior written consent of the Protocol Chair (or her designee).

Record Retention

Following closure of the study, each participating center will maintain a copy of all site study records in a safe and secure location. Investigator records should be maintained for a minimum of 7 years after completion or discontinuation of the study or for longer if required by applicable local regulations.

Additional Information

Each participating site is responsible for submitting additional information as requested by the Protocol Chair (or her designee). The Coordinating Center may terminate the study at a participating site in the event that these conditions are not followed.

10. DATA MANAGEMENT

Data will be scanned to Coordinating site. Site personnel will review and issue queries as needed. Electronic data queries stating the nature of the problem and requesting clarification will be created for discrepancies and missing values. Designated investigator site staff are required to respond promptly to queries and to make any necessary changes to the data. Concomitant treatments and prior medications entered into the database will be coded using the WHO Drug Reference List, which employs the Anatomical Therapeutic Chemical classification system. Medical history/current medical conditions and adverse events will be coded using the Medical dictionary for regulatory activities (MedDRA) terminology. Laboratory samples for hematology, biochemistry, liver function tests, urinalysis, and coagulation will be performed locally. The occurrence of any protocol violations will be determined. After these actions have been completed and the data has been verified to be complete and accurate, the database will be declared locked

11. EVALUATION AND CALCULATION OF VARIABLES

11.1 Calculation or derivation of efficacy variable(s)

The primary objectives of the study are descriptive assessments of ESR1 mutation detection in plasma. One of the secondary endpoints of the study is PFS. PFS is defined as the duration of time from time of randomization to time of progression or death, whichever occurs first. PFS for a subject without an event will be censored on the date of last tumor assessment. If an interval of 6 months passes without a tumor assessment, PFS will be censored at the time of the earlier tumor assessment, even if an event (progressive disease or death) is later observed. If a patient has not had an event, PFS will be censored at the date of the last adequate tumor evaluation. PFS will also be censored at the date of tumor evaluation when the next tumor evaluation (or death) is >6 months after the previous evaluation without an event. PFS will be assessed via local radiology assessment according to RECIST 1.1.

Although central review may occur as part of site calibration or an audit, the local assessment will be considered as the basis for the primary efficacy analysis. In the absence of measurable disease at baseline, the following criteria (per RECIST 1.1) will be used to assess disease progression among the patients with nonmeasurable lytic or mixed (lytic + blastic) bone lesions: 1) The appearance of one or more new lesions or 2) Unequivocal progression of existing non-measurable lesions.

Additional secondary endpoints include response rate, clinical benefit rate, (defined as CR+PR+ SD at any tumor assessment), clinical benefit rate at 6 months (CBR6), in the entire cohort, and the ESR1-mut cohorts. Response rate will be reported from best overall response according to RECIST 1.1 and as described in section 6.3. The response rate will then be compared amongst the tamoxifen plus palbociclib and fulvestrant plus palbociclib arms in the entire cohort and in the subgroup of ESR1-mt patients.

ESR1 mutation will be analyzed both from tumor biopsies and peripheral blood circulating tumor DNA. These tumor biopsies and peripheral blood circulating tumor DNA will be assessed for the following most commonly described ESR1 mutations using Sanger sequencing of the three ESR1 exons which will assess for 23 different ESR1 mutations including the 6 most commonly described (S463P, L536Q, Y537S, Y537C, Y537N, and D538G). Next generation sequencing (NGS) and/or digital droplet PCR (ddPCR) of blood and tumor specimens will also be performed to look at co-existent mutations. It will then be reported as the frequency of occurrence of ESR1 mutation in the cohort of enrolled patients as well as in the cohort of patients treated with fulvestrant plus palbociclib and tamoxifen plus palbociclib.

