5.2.2 Doses and treatment regimens

Fulvestrant Arm

1. Loading dose: Patients will receive a loading dose of 500mg of fulvestrant administered as two 250 mg intramuscular (IM) injections, one into each buttock, on day 1 and day 15.
2. Maintenance Dose: Patients will receive fulvestrant 500mg IM administered as two 250mg intramuscular (IM) injections, one into each buttock, once every 4 weeks starting on day 29. Each cycle will consist of 28 days during which fulvestrant will be administered on day 1.
3. Palbociclib dose: Patients will receive 125mg PO days 1-21 of a 28 day cycle.

Tamoxifen Arm

1. Patients will receive tamoxifen 20mg PO daily
2. Palbociclib dose: Patients will receive 125mg PO days 1-21 of a 28 day cycle.

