6.3 Efficacy

Response and progression will be evaluated in this study using the international criteria proposed by the revised Response Evaluation Criteria in Solid Tumours (RECIST) Committee (version 1.1). Changes in only the largest diameter (unidimensional measurement) of the tumor lesions are used in the RECIST criteria. Patients will be evaluated for response after every 2 cycles of therapy. In the case of non-measurable disease (as defined in 6.3.2), progression of disease will be determined by the appearance of new metastatic lesions or clinical worsening secondary to the non-measurable metastatic site at the treating physician's discretion.

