- Complete Response (CR): Disappearance of all non-target lesions and normalisation of tumor marker level. All lymph nodes must be non-pathological in size (<10mm short axis).
- Non-CR/Non-PD: Persistence of one or more non-target lesion(s) and/or maintenance of tumor marker level above the normal limits.
- Progressive Disease (PD): Unequivocal progression of existing non-target lesions. (Note: the appearance of one or more new lesions is also considered progression).

Evaluation of Best Overall Response

The best overall response is the best response recorded from the start of the treatment until disease progression/recurrence (taking as reference for progressive disease the smallest measurements recorded since the treatment started). The patient’s best overall response assignment will depend on the findings of both target and non-target disease and will also take into consideration the appearance of new lesions.

TABLE 2. Time to response definition

Target Lesions	Non-Target Lesions	New Lesions	Overall Response
-----------------------	---------------------------	--------------------	-------------------------

CR	CR	No	CR
CR	Non CR/Non PD	No	PR
CR	Not evaluated	No	PR
PR	Non PD or not all evaluated	No	PR
SD	Non PD or not all evaluated	No	SD
Not all evaluated	Non PD	No	NE
PD	Any	Yes or no	PD
Any	PD	Yes or no	PD
Any	Any	Yes	PD

CR= complete response, PR= partial response, PD= progressive disease, SD= stable disease, NE= not evaluable.

Note: Patients with a global deterioration of health status requiring discontinuation of treatment without objective evidence of disease progression at that time should be reported as “*symptomatic deterioration*”. Every effort should be made to document the objective progression even after discontinuation of treatment.

Progression Free Survival

PFS is defined as the duration of time from time of randomization to time of progression or death, whichever occurs first. PFS for a subject without an event will be censored on the date of last tumor assessment. If an interval of 6 months passes without a tumor assessment, PFS will be censored at the time of the earlier tumor assessment, even if an event (progressive disease or death) is later observed.

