- L) Fulvestrant will be dosed as follows: 2x250 mg injections on days 1, 15, 29, then next in 4 weeks (day 57) and continuing every 4 weeks thereafter. Tamoxifen will be dosed as follows: Tamoxifen 20mg PO Daily.
- m) All subjects must have a final toxicity assessment at least 30 days following the last dose of study drug
- n) Subjects will be followed approximately every 3 months after completion of study treatment for disease status and survival until death through clinic visit, phone call or record review.

- o) Optional tumor biopsy will be performed \leq 30 days prior to first day of treatment and within 30 days of treatment discontinuation.
- p) Palbociclib will be dosed 125mg PO QD days 1-21 of 28 day cycle
- q) PT, INR, PTT only needs to be repeated for optional biopsies if the patient on anticoagulants

(X) = OPTIONAL

Note: Additional tests may be performed at the discretion of the treating investigator as clinically indicated. The sample collection schedules outlined above are based on an ideal subject. The sample schedule should be followed as closely as is realistically possible; however, the schedule may be modified due to problems such as scheduling delays or conflicts (e.g., clinic closure, poor weather conditions, vacations, etc.).

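### The 6-month gap rule censors PFS before the gap even when the next scan is clean, and section 11.1 gives a second, conflicting censoring date

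*Combined protocol and SAP*

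**What the plan says.** - Section 6.3.4 (Progression Free Survival), repeated in section 11.1: "If an interval of 6 months passes without a tumor assessment, PFS will be censored at the time of the earlier tumor assessment". Section 11.1 adds that this holds "even if an event (progressive disease or death) is later observed".
- Section 11.1 then restates the rule with a different trigger. PFS is "censored at the date of tumor evaluation when the next tumor evaluation (or death) is >6 months after the previous evaluation", with a closing qualifier about being without an event.
- Section 11.1 also has a general rule: "PFS for a subject without an event will be censored on the date of last tumor assessment". It repeats this a little later, referring to the last adequate evaluation.
- Section 6.3: "Patients will be evaluated for response after every 2 cycles of therapy". Section 5.2.2: "Each cycle will consist of 28 days". On treatment, scans are therefore 8 weeks apart.
- Section 9.1, Table 4, marks CT as optional in the off-treatment and follow-up columns. Footnote n: "Subjects will be followed approximately every 3 months after completion of study treatment for disease status and survival until death". That contact may be a visit, a phone call or a record review.
- Section 12.1 calls fulvestrant promising if the fitted PFS hazard ratio is below 0.8 overall, or below 0.65 in the ESR1-mutant subgroup. It gives no sensitivity analysis for PFS censoring.

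**The concern.** A missed-assessment rule is there because progression first seen after a long gap has an uncertain date. If the first scan after the gap shows no progression, that uncertainty is gone: the patient was progression-free throughout. Neither version of the rule makes this distinction. Both discard the documented progression-free time and any later event, even one with a clean scan shortly before it.

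The general rule then gives a different censoring date for a patient with a gap, later clean scans and no event. Two analysts following section 11.1 could build different PFS datasets. At stake are the hazard ratios behind the 'promising' calls and the section 12.1 Cox model that relates circulating ESR1 levels to PFS.

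**Working it through.** The plan states no figure that depends on this rule: 40 patients is an external constraint (section 12.2), with no event count, alpha or power. The check therefore applies the rule to records and then estimates its size under assumptions.

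**1. When the rule applies on treatment.** Missing k consecutive 8-weekly scans leaves a gap of (k + 1) × 56 days.
- k = 2: 3 × 56 = 168 days, under 6 months (about 183 days).
- k = 3: 4 × 56 = 224 days, over 6 months.

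Three consecutive scans must be missed.

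**2. Worked records (weeks).**

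| Record | Gap rule as written | Follow-up continued after a clean scan |
|---|---|---|
| Clean at 8, 16, 24, 56; progression at 64 | Censored at 24 | Event at 64 (64 − 24 = 40 weeks and one event restored) |
| Clean at 8, 40, 48, 56; no event | Censored at 8 | Censored at 56, as the general rule also says (48 weeks later) |
| Clean at 8; progression at 40 | Censored at 8 | Censored at 8 |

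The second record shows the conflict within section 11.1. The third shows that the two derivations differ only when a clean scan follows the gap.

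The phrase about being without an event, at the end of the restated rule, could describe the earlier evaluation or the gap itself. Neither reading exempts a clean post-gap scan. The two triggers (6 months passing, and more than 6 months) also differ at the boundary.

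**3. Expected size.** Assumptions not in the documents: exponential PFS with median 5, 8 or 11 months; follow-up uniform on 26 to 78 weeks; 8-weekly scans; 5%, 10% or 20% of patients with one three-scan gap, given only to those with at least 40 weeks of follow-up; equal rates in both arms; 4000 simulated trials of 40 patients per scenario.

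| Median, gap rate | Events: written / continued | Patients affected | Person-weeks: written / continued |
|---|---|---|---|
| 5 months, 5% | 29.6 / 29.7 | 0.39 | 1045 / 1062 |
| 8 months, 10% | 22.5 / 22.8 | 1.26 | 1223 / 1278 |
| 11 months, 20% | 17.2 / 17.7 | 3.13 | 1258 / 1394 |

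- Events lost run from 0.1/29.7 = 0.3% to 0.5/17.7 = 2.8%. These are only events that follow a clean post-gap scan.
- Person-time lost runs from 17/1062 = 1.6% to 136/1394 = 9.8%, at about 43 weeks per affected patient.
- The chance of a false 'promising' call at a true hazard ratio of 1 is Φ(ln 0.8 ÷ (2/√d)) for d events. It is 0.319 at d = 17.7 and 0.322 at d = 17.2, a change of 0.003. This captures lost events only, not bias.

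**4. Direction of bias.** The entries are event rates relative to complete scanning, on the same kind of assumptions with 10% to 20% of patients having a gap.

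| Gap mechanism | Written rule | Continue after a clean scan, censor if the first post-gap finding is an event |
|---|---|---|
| Unrelated to outcome | about 1.00 | 0.95 to 0.985 |
| Progression in the gap prompts a scan | 1.02 to 1.07 | 1.005 to 1.013 |

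Counting every event at its documented date stayed within 0.977 to 1.02 in all scenarios and kept the most events. The exact values depend on how gaps are generated; the ordering matters more.

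If prompted-scan gaps occurred only in the tamoxifen arm, a true hazard ratio of 1 would appear as about 1/1.07 = 0.93 to 1/1.02 = 0.98. If they occurred only in the fulvestrant arm, it would appear as 1.02 to 1.07.

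**The case against.** The strongest reply is that the written rule is legitimate. It censors before the gap whatever happened next, so when gaps are unrelated to outcome it costs precision but causes no bias. Continuing follow-up only after a clean scan makes censoring depend on outcome: patients who progress or die in the gap lose their event, while those who stay well keep the whole gap as event-free time. This stands, and the simulation bears it out. A reader might infer that the rule distorts PFS simply because it cuts long times short; the documents do not support that. It overstates the event rate only if gaps depend on outcome, for example when worsening prompts a scan that ends the gap early. Section 6.3 (progression by clinical worsening in non-measurable disease) and the Table 4 note allowing tests as clinically indicated make that plausible, not certain.

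Three other inferences should be resisted.
- Not every gap triggers the rule. Only gaps of about 6 months or more do.
- One skipped off-treatment scan cannot be said to trigger it. Footnote n schedules status contact, not 3-monthly imaging, and CT is optional, so there is no scan interval to skip. Long gaps are plausible there, but their frequency cannot be derived.
- The documents give no basis for a count of affected patients. Any figure rests on an assumed gap rate.

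It can also be said that the gap rule is a specific exception that overrides the general rule. That is a sensible reading, but no sentence sets the precedence. It would settle the conflict, not the loss of later events.

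**Conclusion.** The point holds on the text of sections 6.3.4 and 11.1: a clean scan after the gap does not stop the censoring, and section 11.1 gives two dates for a patient with a gap and no event. The effect is modest. Under the stated assumptions, 0.4 to 3.1 of 40 patients are affected, 0.1 to 0.5 events are lost on average and about 2% to 10% of person-time goes. With equal gap rates the chance of a false 'promising' call barely moves. Unequal gaps in this open-label trial could shift the hazard ratio by several percent if progression prompts scans.

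The ESR1-mutant subgroup has less room. At the 25% prevalence hypothesized in section 6.3.5 it is 0.25 × 40 = 10 patients, so one lost event is at least a tenth of its events. PFS remains a secondary endpoint in a pilot whose primary objectives section 11.1 describes as descriptive. This is a matter to settle before the data are seen, not a threat to the trial.

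**What to change.** Put one rule, identically worded, in sections 6.3.4 and 11.1, with a single definition of the interval (more than 6 months, stated in days):

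> If the first assessment after an interval of more than 6 months shows no progression, follow-up continues and later events count. A subject without an event is censored at the last adequate assessment.

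If progression or death is the first thing documented after such an interval, the existing censoring at the assessment before it can stay. Because that makes censoring depend on outcome, add to section 12.1 a pre-specified analysis that counts all progressions and deaths at their documented dates regardless of gaps. Report the hazard ratio both ways, overall and in the ESR1-mutant subgroup, and state in advance which one is compared with the 0.8 and 0.65 thresholds. Tabulating gaps of more than 6 months by arm would show whether the choice matters.

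The cost is a wording change in two sections and one extra analysis. No new data are needed.

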2.2 Secondary objectives

1. Collection of clinical outcome data in this limited patient population
 - a. Progression free survival (PFS), Objective response rate (ORR) and Clinical benefit rate (defined as CR+PR+ stable disease at any tumor assessment) and clinical benefit rate at 6 months (CBR6) (defined as CR+PR+ stable disease for at least 6 months) in the entire cohort, and the ESR1-mt cohorts
2. Correlation between longitudinal changes in circulating levels of ESR1 mutations and clinical outcome
3. Assessment of concordance of ESR1 status in plasma and biopsy samples
4. Use of cfRNA to determine gene expression in AI resistant mutant ESR1 MBC

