3. STUDY PLAN AND PROCEDURES

3.1 Overall study design and flow chart

Patients with ER+ breast cancer who had 1 to 3 prior lines of endocrine therapy and up to one line of chemotherapy for MBC, excluding fulvestrant and tamoxifen, will be randomized in a 1:1 ratio to receive fulvestrant 500mg IM Q28 days with one extra dose on D15 of the first cycle (as a loading dose) plus palbociclib 125mg/day PO on a 21 days on/7 days off schedule or tamoxifen 20mg PO daily plus palbociclib 125mg/day PO on a 21 days on/7 days off schedule. Patient accrual will be a goal of 40 evaluable at up to 4 sites. At randomization, plasma will

be obtained for evaluation of ESR1-mt and a biopsy will be obtained when possible. During treatment, all patients will undergo ct-DNA ESR1 mutation evaluation every 28 days. Treatment will continue until disease progression or unacceptable toxicity. At the time of disease progression, a second biopsy will be obtained when possible and the last blood drawn for evaluation of ct-DNA ESR1-mt will occur. All tissue obtained will also undergo molecular analysis to determine the activity of mutant ESR1.

[figure not shown]

FIGURE 5. Study Schema

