4. SUBJECT SELECTION CRITERIA

4.1 Inclusion criteria

For inclusion in the study subjects should fulfill the following criteria:

1. Signed informed consent
2. Patients must have histologically or cytologically confirmed invasive breast cancer that is ER+ (>1% staining) with radiographical or clinical evidence of metastatic disease
 - a. Measurable and/or non-measurable disease
3. Prior therapies:
 - a. Patients must have previously received an aromatase inhibitor in the adjuvant, neo-adjuvant or metastatic setting.

- b. Patients must have previously received palbociclib in the adjuvant, neo-adjuvant or metastatic setting. If patient is currently taking palbociclib at time of screening for the trial they may continue taking palbociclib.
 - c. The minimum duration of AI in the adjuvant setting is 2 years.
 - d. There is no minimum duration of AI in the metastatic setting or neoadjuvant setting.
 - e. Patients may have been previously treated with an mTOR inhibitor or other investigational agent in addition to an aromatase inhibitor.
 - f. Prior treatment with tamoxifen is allowed in the adjuvant setting provided that it was followed by a minimum of 2 years of an AI.
4. Brain metastasis is allowed if previously treated, stable and off steroids for a minimum of 56 days
5. Age > 18 years
6. Male or female breast cancer is allowed
7. Patients may be pre- or post-menopausal; pre-menopausal patients must be on ovarian suppression and must be adequately suppressed on LHRH agonists with estradiol levels in the post-menopausal range
 - a. Premenopausal patients cannot be pregnant and must agree to adequate birth control in addition to ovarian suppression. Agreement by the patient and/or partner to use highly effective, nonhormonal form of contraception or two effective forms of non-hormonal contraception. Contraception use should continue during the duration of study treatment and for at least 6 months after the last dose of study treatment.
8. ECOG performance status 0-2
9. Adequate bone marrow function as indicated by the following, within 14 days of enrollment:
 - a. ANC \geq 1500 cells/mm³
 - b. Platelets \geq 100,000 cells/ mm³
 - c. Hemoglobin \geq 9 g/dL
10. Adequate liver function, as indicated by the following, within 14 days of enrollment.
 - a. Total bilirubin \leq 1.5 \times upper limit of normal (ULN)
 - b. AST \leq 1.5 \times ULN
 - c. ALT \leq 2.5 \times ULN

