5.6 Procedures for discontinuation of a subject from treatment

All patients who initiate protocol treatment will be included in the overall evaluation of response as part of the ITT analysis. All reasons for discontinuation of treatment should be documented clearly in the study record. In case of treatment discontinuation due to unacceptable toxicity as defined in section 6.4, the patients will still be included in the overall evaluation of response by ITT. If the study medication is discontinued at the patient's own request, the reason for discontinuation from the study must be documented and the patient followed for outcomes by ITT analysis.

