6.3.4 Response Assessment

Target Lesions

When more than one measurable lesion is present at baseline all lesions up to a maximum of five lesions total (and a maximum of two lesions per organ) representative of all involved organs should be identified as **target lesions** and will be recorded and measured at baseline (this means in instances where patients have only one or two organ sites involved a maximum of two and four lesions respectively will be recorded).

Evaluation of Target Lesions

- Complete Response (CR): Disappearance of all target lesions. Any pathological lymph nodes (whether target or non-target) must have reduction in short axis to <10 mm.
- Partial Response (PR): At least a 30% decrease in the sum of diameters of target lesions, taking as reference the baseline sum diameters.
- Progressive Disease (PD): At least a 20% increase in the sum of diameters of target lesions, taking as reference the smallest sum on study (this includes the baseline sum if that is the smallest on study). In addition to the relative increase of 20%, the sum must also demonstrate an absolute increase of at least 5 mm. (Note: the appearance of one or more new lesions is also considered progression).
- Stable Disease (SD): Neither sufficient shrinkage to qualify for PR nor sufficient

increase to qualify for PD, taking as reference the smallest sum of diameters while on study.

Non-target lesions

All other lesions (or sites of disease) including pathological lymph nodes should be identified as **non-target lesions** and should also be recorded at baseline. Measurements are not required and these lesions should be followed as ‘present’, ‘absent’, or in rare cases ‘unequivocal progression’. In exceptional circumstances, unequivocal progression in non-target lesions may be accepted as disease progression. In addition, it is possible to record multiple non-target lesions involving the same organ as a single item on the case record form (e.g. ‘multiple enlarged pelvic lymph nodes’ or ‘multiple liver metastases’).

When the patient only has non-measurable disease, the increase in overall disease burden should be comparable in magnitude to the increase that would be required to declare PD for measurable disease: i.e., an increase in tumor burden from “trace” to “large”, an increase in nodal disease from “localized” to “widespread”, or an increase sufficient to require a change in therapy.

Evaluation of Non-Target Lesions

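### Clinical benefit rates give no credit to durable control short of CR when disease is only non-measurable, and sections 6.3 and 11.1 disagree on whether clinical worsening alone is a PFS event

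*Combined protocol and SAP*

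**What the plan says.** **Who is in.** Section 4.1 accepts "Measurable and/or non-measurable disease". Section 6.3.5 anticipates some bone-only disease. Section 5.6 states: "All patients who initiate protocol treatment will be included in the overall evaluation of response as part of the ITT analysis".

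**Response categories.** Section 6.3.4 defines PR as "At least a 30% decrease in the sum of diameters of target lesions". SD also appears only under target lesions: neither enough shrinkage for PR nor sufficient "increase to qualify for PD, taking as reference the smallest sum of diameters while on study". Non-target disease can be CR, Non-CR/Non-PD or PD. Table 2 then combines target and non-target findings into the overall response.

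**Endpoints.** Section 11.1 lists "Additional secondary endpoints include response rate, clinical benefit rate, (defined as CR+PR+ SD at any tumor assessment", and section 2.2 lists "clinical benefit rate at 6 months (CBR6) (defined as CR+PR+ stable disease for at least 6 months". Both are to be reported for the entire cohort and the ESR1-mutant cohorts.

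**Progression in non-measurable disease.** Section 6.3 accepts new lesions or "clinical worsening secondary to the non-measurable metastatic site at the treating" physician's discretion. Section 11.1 says that PFS is assessed by local radiology under RECIST 1.1. For non-measurable lytic or mixed bone lesions it names two criteria: new lesions, or unequivocal progression of existing ones. Section 12.1 calls fulvestrant promising if the fitted PFS hazard ratio is below 0.8 (unselected population) or below 0.65 (ESR1-mutant).

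**The concern.** There are two separate problems of endpoint scoring.

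(a) A patient with only blastic bone metastases, controlled for a year without CR, has no target lesion and so can be neither PR nor SD as those terms are defined. If the definitions are followed, this patient adds nothing to CBR or CBR6. If a site writes SD on the form, the same patient counts. The reported rate then depends on a coding choice that the protocol does not make, in a trial with "Patient accrual will be a goal of 40 evaluable at up to 4 sites".

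(b) A patient with non-measurable disease who worsens clinically from that disease, with no radiological change, has progressed under section 6.3. Under the radiology sentence in section 11.1, the same patient has not. The trial is open label, local assessment governs, and the PFS hazard ratio feeds the rule in section 12.1, so the event definition should be the same wherever it is read.

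**Working it through.** The plan gives no expected CBR, no share with only non-measurable disease and no power figure, so there is no stated number to reproduce. The check is a reading of the definitions, followed by illustrations on stated assumptions.

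**Table 2, row by row, for a patient without target lesions**

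- Seven of the nine rows need a target-lesion finding (CR, PR, SD, PD or not all evaluated). None of these applies.
- The other two rows accept any target status. One requires non-target PD and the other a new lesion. Both give PD.
- So no row yields CR, PR or SD. CR is reachable only through the separate non-target definition. Persistent disease is Non-CR/Non-PD, and no passage maps that to SD or to clinical benefit.

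**Size for CBR6**

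Assumptions: share *s* with only non-measurable disease is 20–40% (8–16 of 40); true CBR6 *p* is 30% or 50%, equal in both disease types; no CR among these patients; *f* is the fraction of them scored as no benefit.

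Reported CBR6 = *p* × (1 − *s* × *f*)

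| True CBR6 | *f* = 1 (worst case) | *f* = 0.5 | *f* = 0 (all coded SD) |
|---|---|---|---|
| 30% | 0.30 × 0.8 = 24%; 0.30 × 0.6 = 18% | 0.30 × 0.9 = 27%; 0.30 × 0.8 = 24% | 30% |
| 50% | 0.50 × 0.8 = 40%; 0.50 × 0.6 = 30% | 0.50 × 0.9 = 45%; 0.50 × 0.8 = 40% | 50% |

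Expected number of patients whose CBR6 status turns on the coding = 40 × *s* × *p*:

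- true 30%: 40 × 0.2 × 0.3 = 2.4 to 40 × 0.4 × 0.3 = 4.8
- true 50%: 40 × 0.2 × 0.5 = 4 to 40 × 0.4 × 0.5 = 8

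One recoded patient moves the whole-cohort rate by 1/40 = 2.5 points. If 25% carry an ESR1 mutation, as section 6.3.5 hypothesises, that cohort has 40 × 0.25 = 10 patients and one recoded patient moves its rate by 10 points.

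**Progression, side by side**

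| Section | What counts in non-measurable disease |
|---|---|
| 6.3 | New lesions, or clinical worsening from the non-measurable site, as the treating physician judges |
| 11.1 | Local radiology; for lytic or mixed bone lesions, new lesions or unequivocal progression |

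**Size for PFS**

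This was simulated on assumed inputs: 1,500 trials per scenario, 20 per arm, exponential PFS with tamoxifen-arm median 4, 7 or 11 months, true hazard ratio 1.0 or 0.8, 18-month accrual, analysis 6 months after last entry, 8-week scans, *s* = 20% or 40%, and half of these patients worsening clinically one scan before radiological progression in both arms.

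- Patients still scanned after clinical worsening: the median hazard ratio differs between the two rules by at most 0.007, and the below-0.8 verdict differs in about 2–5% of trials.
- Patients censored at clinical worsening, with no later progression documented: at most 0.013, and about 8–16%. This is an upper bound, because the note to Table 2 asks that objective progression still be sought.
- For scale, a fitted hazard ratio below 0.8 arises by chance in 22–29% of trials when the true value is 1.0.

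**The case against.** The strongest reply is that this is loose wording on secondary endpoints of a 40-patient pilot whose primary objectives are descriptive. Several parts of that reply stand.

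- **Unassigned is not failed.** Table 2 leaves these patients without a category; it does not call them failures. Section 2.2 writes stable disease without tying it to target lesions, and sections 6.3 and 11.1 adopt RECIST 1.1 by reference. A site may well code SD, in which case nothing is lost. The protocol's own text still does not say so.
- **Existing controls.** Forms receive central review (6.2), discrepancies are queried (10), and central review may be used to calibrate sites (11.1). These help consistency, but reviewers need a written rule to apply. The CRFs are not in the documents, so they may already hold the needed codes.
- **Bone-only is not the same as non-measurable.** Under 6.3.2, lytic or mixed lesions with a measurable soft-tissue component are measurable. The 20–40% share is therefore purely an assumption.

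Three stronger readings are tempting and are not supported.

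1. *Chance imbalance of these patients between arms distorts the CBR comparison.* The plan specifies no between-arm test of CBR or CBR6; only response rate is compared. Nor would the worst case add noise at these rates. The SE of an arm difference, √(2*p*(1 − *p*)/20), falls from 14.5 points at 30% to 13.5 at 24% and 12.1 at 18%. From 50% it falls from 15.8 to 15.5 at 40% and 14.5 at 30%. The random split is already inside the binomial variance.
2. *The note on symptomatic deterioration contradicts section 6.3.* That note concerns global decline in health without objective progression; section 6.3 concerns worsening from a particular site. Section 6.3.3 also allows clinical examination where lesions cannot be imaged, and 6.3.4 accepts an increase in disease burden large enough to need a change of therapy. The conflict is between 6.3 and 11.1.
3. *Open-label discretion biases PFS towards one arm.* Nothing in the documents shows a direction.

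**Conclusion.** Both parts hold in limited form and should be corrected. (a) Eligible patients with only non-measurable disease and durable control short of CR fall outside CBR and CBR6 as written. Depending on coding, the understatement runs from nothing to 6–12 points at a true CBR6 of 30%, or 10–20 points at 50%. That range rests on the assumed 20–40% share, no CRs among these patients and equal true rates in both disease types. (b) Sections 6.3 and 11.1 can score the same patient differently for PFS. On the assumed inputs the median hazard ratio moves by about 0.01 at most, which is small beside the chance variation of a 20-per-arm comparison. The descriptive ESR1 objectives are not directly affected, and CBR has no decision rule.

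**What to change.** - Add rows to Table 2 for patients with non-target disease only: CR, Non-CR/Non-PD and PD.
- State in 2.2 and 11.1 that Non-CR/Non-PD counts towards clinical benefit, and for CBR6 only if it lasts at least 6 months.
- Reconcile section 6.3 with section 11.1 into one PFS scoring rule for all non-measurable disease, consistent with 6.3.3 and 6.3.4. Which rule to adopt is for the sponsor and investigators.
- Record on the CRF whether each progression was radiological or clinical.
- Add one sensitivity analysis that scores clinical-only progression the other way.

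This concerns endpoint scoring only and changes no treatment decision. The cost is a few lines of protocol text, CRF codes if they are not already there, and one extra analysis. The downside is that, if the reconciled rule is radiological only, patients who worsen clinically and are not scanned again may be censored informatively. The sensitivity analysis would help to show how much that matters.
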